### **Participant inclusion criteria for analysis A**

For each of the 5 index tests, the following criteria will be applied separately:

1. Last FFA result shows no nAMD:

The participant will be included if there is **at least one prior** index test result during the follow-up period.

2. Last FFA result shows nAMD:

The participant will be included if there is an index test result within the previous 3-months. If a participant does not have an index test result within the previous 3-months of their last FFA the FFA will not be considered valid and we will look for an earlier FFA result for the participant and apply rules 1 and 2 again on the earlier FFA.

If no follow-up FFA is available which satisfies either criteria, then the participant will be excluded. If no follow-up FFA is available, the participant will be excluded from the analysis.

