### **Definition of valid follow-up period**

If a participant is included as defined above, then the valid follow-up period will be from baseline until the date of the last valid FFA (as defined above).

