**Table 2 Two by two table: definitions of test and disease status.**

	Index positive	Index negative
Reference standard positive: nAMD	True positives Any reference standard indicates nAMD in study eye AND Any index test result is positive during valid follow-up period	False negatives Any reference standard indicates nAMD in study eye AND Index test negative for all available prior time points
Reference standard negative: No nAMD	False positives All reference standard results indicate no nAMD in study eye AND Any positive index test result during valid follow-up period	True negatives All reference standard results indicate no nAMD in study eye AND Index test negative for all available prior time points

Sensitivity and specificity will be calculated with 95% confidence intervals calculated using the Agresti-Coull method (Zhou 2002). Positive and negative likelihood ratios will also be calculated with 95% confidence intervals calculated using the method in Zhou 2002. Diagnostic odds ratios and the proportion of indeterminate tests will be calculated with 95% confidence intervals. A ROC curve will be plotted and the area under the ROC curve calculated using the trapezoidal rule for visual acuity tests. The standard error for the AUC will be calculated using the method of DeLong, DeLong and Clarke-Pearson (1998) and used to form an asymptotic normal 95% confidence interval.

Monitoring sensitivity and specificity of the tests will be compared using McNemar's statistical test (with 95% confidence intervals produced using Newcombe's method) (Newcombe 1998).

For comparing sensitivities under the primary analysis, the McNemar 2x2 table will be constructed using only patients who have had a positive FFA result. They will be classified as having a positive index test, if the index test has any positive results during the valid follow-up period. They will be classified as having a negative index test, if all prior available tests have been negative during their valid follow-up period. For comparing specificities under the primary analysis, the McNemar 2x2 table will be constructed using only patients who have had negative FFA results throughout using the same index test classification.

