Analysis A2 analysing the index tests collapses the index tests as in table 2 but only uses index tests from the individual's last 6 study months (not the entire study period). A positive index test result out-with the 6 months window therefore does not lead to a positive test result at the collapsed individual

level. The individual diagnostic performance of the tests are calculated using this index test definition and the McNemar comparisons of sensitivity and specificity as detailed above.

The third approach to the index tests uses the index test at the individual's last study visit only (Analysis A3). If a participant developed nAMD according to the reference standard during the follow-up period, only the index test data from their visit where nAMD was diagnosed will be used. If they did not develop nAMD during the follow-up period, index test data from the last visit for which their reference standard is available will be used.

Analyses A1, A2 and A3 use the local FFA as assessed by the responsible ophthalmologist as the reference standard. If a participant has a negative local FFA result but exits the study at that point because of a clinical diagnosis of nAMD by the ophthalmologist, then they will be classified as reference standard no nAMD.

Alternative person level diagnostic accuracy analyses are planned that will use two alternative reference standards:

- An alternative reference standard using the FFA result as determined by the reading centre (analysis A4 using all valid index test results, analysis A5 using index tests from the last 6 months and analysis A6 using the index test results from the last visit). Analyses A4, A5 and A6 comprise the individual diagnostic performances of the tests and the McNemar comparisons.
- An alternative clinical reference standard will also be used. A positive clinical reference standard result will be assigned if there is either a positive local FFA or a positive clinical diagnosis. A negative clinical reference standard result will be assigned if there is a negative FFA or an inconclusive local FFA and negative clinical diagnosis or FFA not done and a negative clinical diagnosis. Analysis A7 will use the clinical reference standard as defined above and all the valid index test results will be used. The individual diagnostic performances of the index tests and McNemar comparisons will be included.

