A summary of the reference standard and index test definitions and the corresponding analyses is included below

Reference standard definitions:

A = Local FFA. Reference standard is positive if the local FFA indicates nAMD. Reference standard is negative if local FFA indicates no nAMD throughout.

B = Reading centre FFA. Reference standard is positive if the reading centre FFA indicates nAMD at any time point and negative if it indicates no nAMD throughout.

C = Clinical reference standard. Reference standard is positive if the local FFA indicates nAMD or a clinician diagnosis of nAMD at any time point. Reference standard is negative if the local FFA is negative/inconclusive/not done and the clinician diagnosis is negative.

Index test definitions:

A = Collapsed index test results from whole valid follow-up period. Positive if there is any positive index test and negative if the index test is negative throughout. All index tests during the valid follow-up period are used.

B = Collapsed definition from last 6 months of monitoring. Only uses index tests within 6 months of participant's study end date. Positive if there is any positive index test within the final 6 months and negative if the index test is negative throughout the final 6 months.

C = Index test result at participant's last available visit only (within a 3 month window of the last FFA).

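### In secondary analyses A7, A2 and A5 the index-test window is not tied to the date of the reference result being used

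*SAP*

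**What the plan says.** **A7.** The definitions before SAP Table 3 make the clinical reference standard (definition C) positive on a positive local FFA or on a clinician's diagnosis at any time. It can be negative when the FFA was inconclusive or not done. On index results the SAP says: "Analysis A7 will use the clinical reference standard as defined above and all the valid index test results will be used". Table 3 assigns A7 index definition A, the whole valid follow-up period. Under the SAP heading on that period, "the valid follow-up period will be from baseline until the date of the last valid FFA". The inclusion criteria, headed for all of analysis A, add: "If no follow-up FFA is available, the participant will be excluded from the analysis".

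**A2 and A5.** Both use index definition B: "Collapsed definition from last 6 months of monitoring. Only uses index tests within 6 months of" the participant's study end date. The reference is the local FFA in A2 and the reading-centre FFA in A5. The text on A2 also says its results are collapsed in the manner of Table 2, where a true positive needs this: "Any index test result is positive during valid follow-up period".

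**When FFAs occur.** Any positive index test should trigger one, and non-converters have one at 18 months and at exit (SAP, Design). Two rules can move the reference to an earlier FFA. A positive FFA with no result for that index test in the previous 3 months is set aside for an earlier one (inclusion criteria). A missing or indeterminate last FFA is replaced by the previous one (missing-data section, stated for A1).

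**The concern.** In an accuracy analysis collapsed over time, the index results should come from the period leading up to the reference result. Definition A does this for an FFA reference, because its period closes at the FFA. Definition B closes at another date, and A7 pairs an FFA-based period with a reference that need not be an FFA.

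A7 is the only accuracy analysis that uses the clinical standard, so it is the only one that can recover nAMD diagnosed without a positive local FFA. If its rules remove those participants or their diagnosing visits, it cannot serve as a check on A1. For A2 and A5, two programmers could follow the text faithfully and produce different 2x2 tables.

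**Working it through.** **The plan's own figure.** Inputs from the SAP sample size section: two-sided 5%, 90% power, difference 0.15, disagreement 0.30, incidence 28%, loss 12%.

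- (1.96√0.30 + 1.2816√(0.30 − 0.15²))² / 0.15² = 136 converters; 136/0.28 = 486.
- The simpler (1.96 + 1.2816)² × 0.30 / 0.15² gives 141 converters; 141/0.28 = 504.
- The stated 491 lies between them, within 3% of each. 491/0.88 = 558, against 560 stated.
- Expected cases: 491 × 0.28 = 137.5, taken as 138.

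Nothing below changes the sample size; only the 138 is carried forward.

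**A7, following the SAP for a participant diagnosed clinically:**

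| FFA situation | Result under the SAP |
|---|---|
| Negative FFA at the diagnosing visit | Period runs to that visit; nothing lost |
| Earlier valid FFA; FFA at diagnosis indeterminate or not done | Period ends at the earlier FFA; diagnosing visit lost |
| No follow-up FFA at all | Excluded, although definition C can classify the participant |

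In the second row a diagnosis at month 30 after a month-18 FFA loses the index results after month 18. The participant is then a false negative on any test that was not positive by month 18. The SAP expects diagnoses of this kind: its dummy table for the local FFA at study exit lists clinical diagnosis among the reasons for a missing result.

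*Assumed worst case.* Suppose k such cases are retained and none was positive earlier on the test. True positives stay at 0.80 × 138 = 110.4.

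- k = 10: 110.4/148 = 74.6%
- k = 20: 110.4/158 = 69.9%

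**A2 and A5, last valid FFA at month 18:**

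| Exit month | Definition B window (months) | Months after the FFA | Months left under Table 2 |
|---|---|---|---|
| 20 | 14–20 | 2 | 4 |
| 22 | 16–22 | 4 | 2 |
| 24 | 18–24 | 6 | 0 |
| 30 | 24–30 | 6 | 0 |

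On the literal reading of definition B, results from after the FFA are compared with it. On the Table 2 reading they are removed, but the window shrinks and then empties. The inclusion rule still admits such a non-converter, and the SAP does not say how an empty window is scored.

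Two further routes lead to the same mismatch:

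- **A positive FFA set aside.** If a positive FFA at month 30 ends monitoring but is rejected for lack of an index result in months 27–30, the window of months 24–30 can still hold results from months 24–27. These are then compared with an earlier FFA.
- **A5 only.** A reading-centre positive on an FFA read locally as negative does not by itself end monitoring. If that FFA is at month 18 and the participant stays to month 36, the window is months 30–36. It starts 12 months after the reference turned positive.

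**Scale for A2.** Assume 560 enrolled, scheduled FFAs only, and no triggered or exit FFA in those who leave.

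| Loss assumption | Leave in months 18–36 | Of these, after month 24 |
|---|---|---|
| 12% over 36 months, uniform | 560 × 0.12 × 18/36 = 33.6 | 560 × 0.12 × 12/36 = 22.4 |
| 12% over 36 months, constant hazard | 560 × (0.88^0.5 − 0.88) = 32.5 | 560 × (0.88^(2/3) − 0.88) = 21.5 |
| 10% per year (SAP background gives this as an upper bound on dropout) | 560 × (0.9^1.5 − 0.9³) = 69.9 | 560 × (0.9² − 0.9³) = 45.4 |

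**The case against.** The strongest reply is that the design normally makes the dates agree. A late positive index test should trigger a new FFA, which becomes the last one; the one written exception is narrow (Protocol 3.2.3, further acuity loss after a negative triggered FFA). Monitoring ends at diagnosis, and non-converters have an exit FFA. Protocol section 8 itself mentions study completion in its example of a 6-month window, although it ties the window to the positive reference result. All of this stands, and it narrows the A2 problem to participants with neither a usable triggered FFA nor a usable exit FFA, plus the rejected-FFA route. It does not remove the problem: the internal pilot criteria (Protocol 7.3) allow for positive tests not followed by an FFA request. Nor does it answer the A5 route or A7.

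Two stronger readings are tempting, and the documents do not support them:

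- **That 12% of 560, or 67 participants, are affected in A2 and A5.** That allowance also covers indeterminate and missing results. Leavers with no follow-up FFA are excluded, so no mismatch arises for them.
- **That A7 makes every clinically diagnosed case a false negative on all tests.** An earlier positive on a test keeps it a true positive, a negative FFA at the diagnosing visit keeps that visit, and participants with no follow-up FFA leave the denominator.

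The paired comparisons also suffer less than the single sensitivities. False negatives shared by both tests leave McNemar's discordant counts unchanged, and a 15-point difference would shrink to 0.15 × 138/148 = 14.0 points (k = 10) or 0.15 × 138/158 = 13.1 points (k = 20).

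**Conclusion.** The point holds for secondary analyses A7, A2 and A5, and it should be corrected before analysis. A reader might infer that the primary result is at risk. It is not, because A1 takes both its reference and its index period from the local FFA.

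For A7 the contradiction is in the text and needs no assumption to establish. Its size cannot be derived, because the documents give no number of clinical diagnoses without a valid FFA at that time. The values 74.6% and 69.9% are floors for chosen values of k, not forecasts.

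For A2 and A5 the anchor is undefined, and in A2 it conflicts with Table 2. About 33 to 34 participants leaving after month 18, of whom 21 to 22 leave after month 24, illustrates the exposure in A2 at 12% loss. It rests on there being no triggered or exit FFA in those participants, so triggered or exit FFAs would reduce it. The number affected through reading-centre disagreement in A5 cannot be derived either.

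**What to change.** End the index window in each analysis at the date of the reference result actually used:

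- **A2:** the last valid local FFA.
- **A5:** the first positive reading-centre FFA, or the last valid one if all are negative.
- **A7:** the earlier of a positive local FFA and a clinical diagnosis, or the last clinical assessment if neither occurred.

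Reword definition B as index results within the 6 months before that date. Give A7 its own inclusion rule in place of the FFA-based one: at least one follow-up index result and a determinate status under definition C, with valid follow-up running to the date above.

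The cost is SAP wording and programming with FFA, visit and diagnosis dates, and no new patient procedures. The SAP already needs such dates for its time-to-conversion analysis and its table of intervals between index tests and the last FFA.

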**Table 3 Description of the different reference standard and index test results definitions for analysis A**

Analysis number	Analysis	Reference standard definition of disease	Index test definitions
A1 (Main analysis)	Primary diagnostic analysis-diagnostic performance of the individual tests. Paired comparison (McNemar) of sensitivity and specificity between the tests.	A	A
A2	Secondary diagnostic analysis-diagnostic performance of the individual tests. Paired comparison (McNemar) of sensitivity and specificity between the tests.	A	B
A3	Secondary diagnostic analysis-diagnostic performance of the individual tests. Paired comparison (McNemar) of sensitivity and specificity between the tests.	A	C
A4	Secondary diagnostic analysis-diagnostic performance of the individual tests. Paired comparison (McNemar) of sensitivity and specificity between the tests.	B	A
A5	Secondary diagnostic analysis-diagnostic performance of the individual tests. Paired comparison (McNemar) of sensitivity and specificity between the tests.	B	B
A6	Secondary diagnostic analysis-diagnostic performance of the individual tests. Paired comparison (McNemar) of sensitivity and specificity between the tests.	B	C
A7	Secondary diagnostic analysis-diagnostic performance of the individual tests. Paired comparison (McNemar) of sensitivity and specificity between the tests.	C	A

**Analysis B. The secondary complex analysis which utilises repeated test results.**

Analysis B will use reference standard definition A (local FFA result will be reference standard).

A GEE modelling approach will be used to allow the simultaneous modelling of sensitivity and specificity in a regression framework and use of multiple test results per participants over time. A GEE modelling has the advantage of allow a flexible regression framework (with easy comparison between tests), allowing for clustering of observations by participants and incomplete data without only requiring extensive distributional assumptions. The GEE modelling will be applied using the local FFA finding as the reference standard. It will be assumed that at time

points when index tests are available but the reference standard was not available, the result is negative until negative positive reference standard finding.

**Analysis C. Person level diagnostic accuracy analyses using a combination of tests.**

Analysis C will use a combination of tests under a simple approach (i.e. positive if either index test is positive), instead of a single test under the diagnosis analysis approach. Specifically, the impact of combining OCT with fundus evaluation, Amsler test, patient’s subjective assessment of vision, or visual acuity tests will be considered. For the “both positive” approach there will need to be a prior visit where both of the index tests were positive to define a positive result and there will be a negative result if there are no prior visits where both the index tests are positive. For the “either positive” approach there will need to be at least one prior positive index test result from either of the tests to define a positive result and no prior positive index test results from both of the tests to define a negative result. The reference standard and index tests result will match the definition of Analysis A1, using all valid index test results, with the additional step of generating an overall combination test result.

**Analysis Objective 2: To develop a risk prediction model**

**Analysis D. Prognostic modelling.** A risk prediction model using Cox regression will be developed to predict development of nAMD (using the clinical reference standard – see reference standard definition C above in table 3) in the EDNA study eye using baseline risk factors. Appendix 1 shows the table of risk factors which will be considered for inclusion in the model. The model’s predictive performance will be assessed in terms of discriminative and calibrative ability. Discriminative ability will be assessed using Harrell’s *c*-index. Calibration will be assessed by plotting the average predicted risk compared with the corresponding Kaplan-Meier estimate of the observed risk by tenth of predicted risk. Recalibration of the model will be undertaken via adding/removing predictors if necessary. Internal validation will be undertaken using a bootstrapping approach. (Moons 2012).

**Analysis Objective 3: Quantify the time to and risk of conversion**

**Analysis E. time-to-conversion distribution.** The survival distribution of conversion to nAMD (defined as local FFA conversion in a first analysis; and as the clinical diagnosis in a second analysis) over the follow-up period will also be estimated. Participants that did not convert will be censored at the time of their last available observation. First, a Kaplan-Meier curve will be fitted to estimate the underlying nAMD conversion distribution. Second, time of conversion will be estimated based upon the date of conversion confirmation. The distribution will be estimated

assuming parametric distributions and addressing the interval nature of the data. This will be done using the *stintreg* command in Stata. Exponential, Weibull and log-normal proportional hazard survival models will be fitted. Furthermore, using an accelerated time failure approach, a generalised gamma distribution will also be used. Related assessments of fit will be summarised.

**Analysis Objective 4:** To explore the impact of CNV subtype on time to conversion

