### **Safety data**

Within the EDNA study we will record only any AE/SAE relating to collection of blood or FFA requested during involvement in the study. AEs relating to FFAs conducted prior to recruitment to the study will not be reported.

Any AE/SAE resulting from treatment to the nAMD eye during the study will not be recorded as an AE/SAE. Once an EDNA participant has nAMD in the study eye, or the end of follow-up, any subsequent AE or SAE will not be recorded.

In this study the only AE and SAE that are expected relate to the collection of blood and the FFA.

FFA related expected adverse events: These may be local skin irritation, development of erythematous lesions on the skin immediately after FFA and more generalised reaction to the FFA with pulmonary and or other systemic manifestations (anaphylaxis)

Blood collection expected adverse events: bruising and discomfort at the site of any puncture.

Most participants in the study will be elderly, and we anticipate that 50% will be >75 years at the time of recruitment. Therefore it is expected that a proportion of the cohort will die from causes unrelated to the study over the period of follow up. Deaths unrelated to the study procedures will not be recorded as SAEs but will be recorded within the CRF.

## Appendix 1

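### With deaths censored, the Kaplan-Meier and Cox analyses give a net conversion risk that is somewhat too high when read as a patient's absolute risk, and the planned calibration plot cannot show it

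*SAP*

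**What the plan says.** SAP Analysis Objective 3 is headed "Quantify the time to and risk of conversion". Under Analysis E, "First, a Kaplan-Meier curve will be fitted to estimate the underlying nAMD conversion distribution", and parametric interval-censored models follow. The only censoring rule is "Participants that did not convert will be censored at the time of their last available observation"; death has no rule of its own. The event is "defined as local FFA conversion in a first analysis; and as the clinical diagnosis in a second analysis".

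Analysis D builds a Cox model from baseline factors, with the event defined "using the clinical reference standard" (a positive local FFA or a clinician diagnosis). On calibration it states: "Calibration will be assessed by plotting the average predicted risk compared with the corresponding Kaplan-Meier estimate of the observed risk by tenth of predicted risk".

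The SAP section on safety data expects half the participants to be over 75 at recruitment and says "it is expected that a proportion of the cohort will die from causes unrelated to the study over the period of follow up". Deaths are to be recorded in the CRF. Neither document mentions competing events or a cumulative incidence function. The one survival sensitivity analysis moves the conversion date to midway between the positive FFA and the previous negative one.

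Two uses of these results are named. Protocol section 10 wants the conversion distribution and the risk model to support risk assessment in managing individual patients and to inform the monitoring interval. Protocol section 9 feeds time-to-event results into an economic model that takes mortality separately from life tables.

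**The concern.** A participant who dies unconverted can no longer convert. Kaplan-Meier treats that person as someone who would have gone on to convert at the same rate as those still followed. The resulting curve describes conversion in a setting without death. This is a legitimate quantity, but it is not the proportion of patients who will convert within three years, and it exceeds that proportion whenever anyone dies first.

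The SAP does not say which of the two it wants, and the two named uses need different ones. Analysis D is where the gap has most effect. An observed risk taken from Kaplan-Meier is one minus the survival estimate, and a Cox model that censors deaths predicts on the same scale. The two sides of the calibration plot therefore share the same upward shift, and perfect agreement between them is compatible with overprediction of absolute risk in every tenth. No other planned check looks for it.

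What is at stake is the absolute risk quoted to clinicians and patients from two secondary analyses.

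**Working it through.** **Inputs**
- Three-year conversion: 28% (SAP, Sample size). Taken here as the net figure, since that is what Kaplan-Meier with deaths censored estimates. The documents do not say whether it is net or crude.
- Cohort size: 560 (same section).
- Three-year mortality: not given. The 12% allowance in the sample size covers indeterminate and missing results as well as loss, so it is not a death rate. A range of 6% to 15% is assumed.
- Constant hazards, with death independent of conversion: assumed.

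**The plan's own figure.** McNemar pairs = (1.960·√0.30 + 1.282·√(0.30 − 0.15²))² / 0.15² = 136, and 136/0.28 = 486, close to the stated 491. Then 491/0.88 = 558 against the stated 560, and 491 × 0.28 = 137 conversions, in line with the anticipated total of over 130. The 28% is therefore used consistently. Nothing in this calculation depends on how deaths are handled in Analyses D and E.

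**Net versus actual risk.** The conversion hazard is l = −ln(0.72)/3 = 0.1095 per year. With 3-year death probability d, the death hazard is m = −ln(1 − d)/3. The proportion who actually convert by three years is

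CIF = l/(l + m) × [1 − exp(−3(l + m))], where exp(−3(l + m)) = 0.72 × (1 − d).

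Example, d = 12%: m = 0.0426; l/(l + m) = 0.720; 0.72 × 0.88 = 0.634; CIF = 0.720 × 0.366 = 26.4%. A simulation of this case gave 28.0% for one minus Kaplan-Meier and 26.4% for the crude proportion.

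The standard error is of Greenwood type: variance = 0.72² × (l/560) × [exp(3(l + m)) − 1]/(l + m).

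| 3-year deaths (assumed) | CIF | Overstatement, points | KM SE, points | Ratio |
|---|---|---|---|---|
| 6% | 27.2% | 0.8 | 1.9 | 0.42 |
| 8% | 26.9% | 1.1 | 1.9 | 0.55 |
| 10% | 26.7% | 1.4 | 2.0 | 0.69 |
| 12% | 26.4% | 1.6 | 2.0 | 0.83 |
| 15% | 26.0% | 2.0 | 2.0 | 1.03 |

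**Variation with risk.** At the same assumed mortality of 4% a year (11.5% over three years), the gap is 0.6 points in a group with 10% net risk, 1.6 points at 28% and 2.6 points at 50%. It also grows with mortality: at 50% net risk it is 1.3 points at 2% a year and 5.1 points at 8% a year. The gap is therefore widest in any group where conversion risk and mortality are both high.

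**The case against.** **The net distribution may be intended.** The SAP speaks of the underlying distribution, its dummy table reports survival probability, and nowhere does it say that one minus Kaplan-Meier will be the headline for Analysis E. The economic model needs this quantity: crude incidence combined with life-table mortality would count death twice. This stands, and is why the existing fits should be kept. It does not answer the point for Objective 3, for protocol section 10, or for Analysis D, where Kaplan-Meier is expressly the observed risk.

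**The monitoring interval concerns living attenders,** for whom the hazard while alive is the relevant input. This also stands. The absolute-risk use that remains is individual risk assessment.

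**The effect is small and rests on assumed mortality.** This is correct. A tenth of 560 is 56 people, so the binomial standard error at 50% is √(0.25/56) = 6.7 points, and a gap of a few points would be hard to see in any single tenth even with the right benchmark. The shift runs in one direction across all tenths, however, and the confidence interval does not account for it.

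**Stronger readings that a reader might infer.**
- *Clinical-diagnosis exits also inflate the risk, hidden by calibration.* The SAP describes an FFA-negative participant who "exits the study at that point because of a clinical diagnosis of nAMD by the ophthalmologist". Such exits are events in Analysis D and in the second Analysis E, so calibration hides nothing about them. They are censored only in the first Analysis E. If they are 5% to 20% of conversions (assumed, deaths ignored), one minus Kaplan-Meier for FFA conversion is 1 − 0.72^0.95 = 26.8% to 1 − 0.72^0.80 = 23.1%. That is 0.2 to 0.7 points above crude FFA incidence (0.95 × 28% = 26.6%; 0.80 × 28% = 22.4%), but 1.2 to 4.9 points below the 28% for any conversion. No general overstatement follows.
- *The top tenth is overpredicted by a known large amount.* The documents give neither risk nor mortality by tenth. Age is one of 21 candidate factors, many of them ocular, so the tenths with the highest predicted risk need not have the highest mortality.

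**Conclusion.** The point holds for deaths, as a modest bias of known direction in secondary objectives. If the curves and predictions from Analyses D and E are quoted as absolute risk, they will be too high by an amount that depends on mortality, which the documents do not give. Across the assumed range this is at most about one standard error for the whole cohort. The figures rest on constant hazards, on independence of death and conversion, and on taking 28% as the net 3-year risk. The direction needs only that some participants die before converting. As a net distribution for the economic model the planned analysis is sound under independence, an assumption the SAP should state. Sensitivity, specificity, the McNemar comparisons and the sample size are not touched.

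**What to change.** - **Analysis E:** name the estimand. Beside Kaplan-Meier, report the Aalen-Johansen cumulative incidence of conversion with death as a competing event, and use it wherever a risk of conversion is quoted.
- **Analysis D:** derive absolute predicted risk from cause-specific Cox models for conversion and for death, and calibrate by tenth against Aalen-Johansen.
- **Economic model:** keep Kaplan-Meier, the cause-specific hazards and the parametric interval-censored fits as its inputs, and say that they describe net conversion.

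The cost is some SAP wording, standard code, a second curve, a death model to fit and a slightly lower reported risk. Dates of death are also needed. The documents say that deaths are recorded in the CRF but do not mention dates, and the present rule uses the last observation instead, so availability should be confirmed before the SAP is changed.
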